## Exploratory biomarkers (central laboratory, please refer to study flowchart in Section 1)

- Tumor biopsy for IHC, CD38, PD-L1, immune contexture.
- Tumor biopsy for transcriptomic analysis.
- Tumor biopsy for genomic characterization (tumor mutational load and MSI status).
- Blood sample for tumor mutational load.
- Blood sample for plasma or serum cytokines.

#### Disease assessment

- Tumor imaging: CT or MRI scan of the chest, abdomen, pelvis and any other locations with suspicion or evidence of disease involvement (the same method of assessment should be used throughout the study). The initial tumor imaging will be performed within 28 days screening period (as close as possible to initiation of IMP). Scans performed as part of routine clinical management are acceptable for use as the screening scan if they are of diagnostic quality and performed within 28 days before IMP initiation.
  - mCRPC: Measureable lesion per RECIST 1.1 per local reading is not mandatory.
  - NSCLC: Patients with NSCLC must have at least 1 radiographically measurable lesion per RECIST 1.1 per local reading.
- Prostate-specific antigen assessment for patients with mCRPC (local laboratory).
- Bone scan for patients with mCRPC: The initial scan will be performed within 28 days screening period (as close as possible to initiation of IMP). Scans performed as part of routine clinical management are acceptable for use as the screening scan if they are of diagnostic quality and performed within 6 weeks before IMP initiation. In case of doubtful lesions on bone scan, bone-centered X-ray or MRI scan should be performed to confirm the nature of those lesions (metastatic or not).

All patients who signed the study informed consent form will be assigned a patient number. Each patient will receive an incremental identification number corresponding to his/her order of enrollment in the study. Those patients, who meet all the inclusion criteria and none of the exclusion criteria, will be eligible for registration in the study. A written confirmation of each eligible patient identification and treatment dose level will be forwarded to the Investigator.

#### 12.3 TREATMENT PERIOD

#### 12.3.1 Cycle 1 (Day 1, Day 8 and Day 15)

The treatment window is  $\pm 1$  day for each of the QW administrations and  $\pm 2$  days for each of the Q3W administrations. The following procedures are to be performed/assessed on Day 1, Day 8 and Day 15 prior to study treatment administration unless specified otherwise:

- Physical examination: includes examination of major body systems (neurological, digestive, respiratory [signs and symptoms, respiratory rate] and lymph node examination).
- Body weight prior to starting infusion.

- Vital signs including blood pressure, heart rate, temperature, and respiration rate, prior to starting infusion of IMP, every hour during infusion, and at the end of infusion, and if clinically indicated during the infusion.
- Performance status (ECOG).
- All AEs/SAEs throughout the cycle, including AEs of new onset as well as worsening of baseline signs and symptoms.
- Concomitant medications from registration and used throughout the cycle.
- Study treatment administration: REGN2810 on Cycle 1 Day 1 (only in cohorts receiving isatuximab and REGN2810 combination); isatuximab on Cycle 1 Day 1, Cycle 1 Day 8 and Cycle 1 Day 15 (isatuximab is not administered on Cycle 1 Day 8 and Cycle 1 Day 15 in Cohort C and Cohort D).

#### Laboratory assessments

- Serum or urine pregnancy test: WOCBP must have a negative serum pregnancy test result within 7 days prior to first IMP administration. A pregnancy test (serum or urine, local laboratory) is to be done on Day 1 of each cycle prior to the study treatment. Pregnancy test is not required at Cycle 1 Day 8 or Cycle 1 Day 15.
- Blood chemistry: includes AST, ALT, bilirubin (total and direct), ALP, LDH, sodium, potassium, chloride, bicarbonate/carbon dioxide, calcium, magnesium, phosphate, uric acid, urea or BUN, serum creatinine, eGFR (MDRD formula; Appendix H), glucose (fasting), albumin, total protein, TSH, and free T4 if TSH is outside of the normal range. To be performed every 7 days in cases of Grade 3 or Grade 4 abnormalities. Blood chemistry assessments are not required to be repeated prior to Cycle 1 Day 1 if performed ≤3 days prior to first study treatment administration at Screening (local laboratory).
- Hematology: includes hemoglobin, hematocrit, RBC, WBC with differential, and platelet counts. If Grade 4 neutropenia, assess ANC every 2 to 3 days until ANC  $\geq 0.5 \times 10^9$ /L and at least weekly thereafter until ANC  $\geq 1.0 \times 10^9$ /L. Hematology assessments are not required to be repeated prior to Cycle 1 Day 1 if performed  $\leq 3$  days prior to first study treatment administration at Screening (local laboratory).
- Quantitative or semi-quantitative urinalysis on Day 1: includes RBC, protein, glucose, pH, ketones, bilirubin, leucocytes, nitrates and specific gravity. To be repeated if hematuria is observed or clinically indicated. Urinalysis assessments are not required to be repeated prior to Cycle 1 Day 1 if performed ≤3 days prior to first study treatment administration at Screening Dipstick (qualitative) will be performed on Day 1 of each new cycle if clinically indicated (local laboratory).
- Blood sample collection for PK and ADA evaluation (see Section 1.5).

## Exploratory biomarkers (central laboratory, please refer to study flowchart in Section 1)

- Blood sample for immune genetic markers (Day 1 only).
- Blood sample for tumor genetic markers (Day 1 only).

- Blood sample for immunophenotyping (Day 1 only).
- Blood sample for plasma or serum cytokines (Day 1 only).

#### Disease assessment

• Prostate-specific antigen assessment on Day 1 for patients with mCRPC. PSA assessments are not required to be repeated prior to Cycle 1 Day 1 if performed ≤3 days prior to first study treatment administration at Screening (local laboratory).

## If clinically indicated only

- 12-lead ECG (single).
- Coagulation: includes prothrombin time or INR and activated PTT (local laboratory).
- Qualitative urinalysis (dipstick) on Day 1 (local laboratory).
- Any other examinations that are clinically indicated.

## 12.3.2 Subsequent cycles (Day 1)

The treatment window is  $\pm 2$  days for each of the Q3W administrations. The following procedures are to be performed/assessed on **Day 1 prior to study treatment administration unless specified otherwise:** 

- Physical examination: includes examination of major body systems (neurological, digestive, respiratory [signs and symptoms, respiratory rate] and lymph node examination).
- Body weight.
- Vital signs including blood pressure, heart rate, temperature, and respiration rate, prior to starting infusion of IMP, every hour during infusion, and at the end of infusion, and if clinically indicated during the infusion.
- Performance status (ECOG).
- All AEs/SAEs throughout the cycle, including AEs of new onset as well as worsening of baseline signs and symptoms.
- Concomitant medications used throughout the cycle.
- Study treatment administration: REGN2810 on Day 1 (only in cohorts receiving isatuximab and REGN2810 combination); isatuximab on Day 1.

#### Laboratory assessments

- Serum or urine pregnancy test for WOCBP: a pregnancy test is to be done on Day 1 of each cycle prior to the study treatment (local laboratory).
- Blood chemistry: includes AST, ALT, bilirubin (total and direct), ALP, LDH, sodium, potassium, chloride, bicarbonate/carbon dioxide, calcium, magnesium, phosphate, uric acid, urea or BUN, serum creatinine, eGFR (MDRD formula; Appendix H), glucose (fasting), albumin, total protein, TSH (every second cycle), and free T4 if TSH is outside of the normal range. To be performed every 7 days in cases of Grade 3 or Grade 4 abnormalities (local laboratory).

- Hematology: includes hemoglobin, hematocrit, RBC, WBC with differential, and platelet counts. If Grade 4 neutropenia, assess ANC every 2 to 3 days until ANC  $\geq$ 0.5 × 10^9/L and at least weekly thereafter until ANC  $\geq$ 1.0 × 10^9/L (local laboratory).
- Blood typing interference test on Cycle 2, Day 1 only (local laboratory).
- Blood sample collection for PK and ADA evaluation (see Section 1.5, central laboratory).

## Exploratory biomarkers (central laboratory, please refer to study flowchart in Section 1)

- Tumor biopsy for IHC, CD38, PD-L1, immune contexture at Cycle 2 Day 1 (≤7 days; after IMP administration on C1D15 wherever applicable, prior to IMP administration on Cycle 2 Day 1), only if clinically feasible.
- Tumor biopsy for transcriptomic analysis at Cycle 2 Day 1 (≤7 days; after IMP administration on C1D15 wherever applicable, prior to IMP administration on Cycle 2 Day 1), only if clinically feasible.
- Blood sample for tumor genetic markers (Cycle 2 Day 1 and Cycle 3 Day 1 only).
- Blood sample for immunophenotyping (Cycle 2 Day 1, Cycle 3 Day 1, then on Day 1 prior to IMP administration at each odd numbered cycle starting from Cycle 5).
- Blood sample for plasma or serum cytokines (Cycle 2 Day 1, Cycle 3 Day 1, then on Day 1 prior to IMP administration at each odd numbered cycle starting from Cycle 5).

#### Disease assessment

- Tumor imaging: CT or MRI scan every 9 weeks starting at the end of Cycle 3 ( $63 \pm 7$  days) and whenever disease progression is suspected (the same method of assessment should be used throughout the study). Tumor imaging timing should follow calendar days and should not be adjusted for delays in cycle starts.
  - If initial evidence of RECIST 1.1 defined progression is documented, patients could continue treatment while waiting for PD confirmation scan 4 weeks after providing the patients are clinically stable as detailed in Section 6.7.1. When treatment is continued beyond RECIST 1.1 defined tumor progression, subsequent imaging assessments should be based upon iRECIST criteria (Appendix D).
  - For patients with mCRPC, bone lesions are not considered "non-measurable" lesion pre RECIST 1.1. Bone lesions will be assessed by bone scan only.
- Prostate-specific antigen assessment every 9 weeks starting at the end of Cycle 3 (63 ±7 days) for patients with mCRPC. Patients with PSA progression (Appendix A) in the absence of radiographic progression should continue IMP (local laboratory).
- Bone scan for patients with mCRPC, every 9 weeks starting at the end of Cycle 3 (63 ±7 days). In cases of PD based on bone scan only, the bone scan should be repeated after 6 weeks to confirm the progression using the 2+2 rule (2 new lesions on first scan, with at least 2 additional lesions on the confirmatory scan; refer to Appendix A) as detailed in Section 6.7.1. In case of doubtful lesions on bone scan, bone-centered X-ray or MRI scan should be performed to confirm the nature of those lesions (metastatic or not).

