# **DURATION OF STUDY PERIOD (per patient)**

The duration of the study for a patient will include a screening period (up to 28 days), a treatment period (up to 2 years), a safety follow-up period (90 days or until negative ADA testing if ADA test is positive or inconclusive at Day 90), and a survival phone call follow-up period (until death or study cut-off).

**Treatment period:** The cycle duration is 21 days. Patients will continue treatment until disease progression confirmed by imaging 4 weeks after initial evidence of progression (radiographic progression of mCRPC defined by bone scan should be confirmed by a second bone scan 6 weeks later also using the 2+2 rule [at least 2 new lesions on first post-treatment scan, with at least 2 additional lesions on the next scan]) providing they are clinically stable, unacceptable AEs, patient's decision, 2 years of IMP treatment without documented PD, or administrative reasons. Patients with PSA progression in the absence of radiographic progression should continue IMP.

**Safety follow-up period:** After treatment discontinuation, patients will return to the study site 30 days ( $\pm 7$  days) after the last dose of IMP, or when the patient receives another anti-cancer therapy, whichever is earlier, for end of treatment (EOT) assessments. In addition, there will be an extended safety follow-up period for 90 days after the last dose of IMP for ADA assessment and for safety assessment. If REGN2810 or isatuximab ADA testing is positive or inconclusive during post treatment follow-up, ADA testing will be repeated every 3 months until negative.

Patients who discontinue the study treatment without PD will be followed every 90 days for disease assessment until confirmation of PD or start of treatment with another anti-cancer therapy, or until study cut-off date, whichever comes first.

**Survival phone call follow-up period:** The further follow-up schedule beyond 90 days after last dose of IMP is according to the disease progression status:

Patients who discontinue study treatment due to PD: phone call follow-up will be done every 90 days from the date of last IMP administration until death or study cut-off date.

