# 6.4 CROSS-OVER PART (A SUBPART OF COHORT A-2)

Patients from Cohort A-2 who progress on isatuximab monotherapy may receive isatuximab plus REGN2810 at the discretion of the Investigators and if they still fulfill the eligibility criteria (except exclusion criteria #3 and #8). The screening period for the cross-over part is 28 days from PD confirmation.

All screening processes for the patients in the Phase 1 and Phase 2 parts are to be conducted before combination IMP initiation for the cross-over part, except informed consent, demography, medical/surgical and disease history, and weight/height. Tumor biopsy at cross-over screening is required unless clinically unfeasible and after discussion with the Sanofi Medical Monitor. On treatment biopsy at Cycle 2, Day 1 (≤7 days; after IMP administration on C1D15 wherever applicable, prior to IMP administration on Cycle 2 Day 1) of the cross-over part is optional (fine

needle aspirate is not acceptable). Patients who are included in the cross-over part should be evaluated as Cohort A-1 and Cohort B (except PK).

Patients who do not meet the cross-over part eligibility criteria should be followed up for safety and survival.

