#### 6.7 DURATION OF STUDY PARTICIPATION

#### 6.7.1 Duration of study participation for each patient

The duration of the study for a patient will include a period of screening of up to 28 days, a treatment period (up to 2 years), a safety follow-up period (90 days or until ADA is negative, if ADA test is positive or inconclusive at Day 90), and a survival phone call follow-up period.

**Treatment period**: The cycle duration is 21 days. Patients will continue treatment until disease progression confirmed by imaging 4 weeks after initial evidence of progression (or 6 weeks for bone progression in mCRPC in Appendix A), unacceptable AEs, patient's decision, 2 years of uninterrupted delivery of IMP without documented progressive disease (PD), or administrative reasons.

Patients who have apparent radiographic progression by CT/MRI per RECIST v1.1 or bone scan per PCWG3 criteria are allowed to continue until PD is confirmed providing:

• Absence of clinical symptoms or signs indicating clinically significant disease progression;

b Isatuximab: the infusion should be completed within 16 hours from the end of infusion preparation or a new infusion should be prepared with the remaining dose to be administered the same day.

- No decline in performance status;
- Absence of rapid disease progression or threat to vital organs or critical anatomical sites [eg, CNS metastasis, respiratory failure due to tumor compression, spinal cord compression] requiring urgent alternative medical intervention;
- No significant, unacceptable or irreversible toxicities related to study treatment.

**Safety follow-up period**: After treatment discontinuation, patients will return to the study site 30 days (±7 days) after the last dose of IMP, or when the patient receives another anti-cancer therapy, whichever is earlier, for end-of-treatment assessments. In addition, there will be an extended safety follow-up period for 90 days after the last dose of IMP for ADA assessment and for safety assessment. If ADA test is positive or inconclusive, ADA testing will be repeated every 3 months until negative. All ongoing related AEs, ongoing SAEs and new related AE/SAEs will also be followed up.

Patients who discontinue the study treatment without PD will be followed every 90 days for disease assessment until confirmation of PD or start of treatment with another anti-cancer therapy, or until study cut-off date, whichever comes first

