## 19 APPENDICES

# Appendix A Prostate Cancer Clinical Trials Working Group 3 criteria for progression

Details provided in bibliographic reference (48).

Response evaluation definition for the primary efficacy endpoint (Table 9):

- In mCRPC: response will be defined per PCWG3 criteria on the basis of the following outcomes (if any of these occur, patients will be considered to have responded):
  - Radiographic objective response assessed and confirmed by the Investigators;
  - PSA decline of ≥50% (confirmed by a second PSA test).

For analysis of DoR (secondary efficacy endpoint), disease progression includes radiographic disease progression or unequivocal clinical progression (Table 9). For patients with mCRPC, radiographic progression includes progression by PCWG3 modified RECIST 1.1 for soft tissue and/or PCWG3 defined progression by bone scan.

Table 9 - Response evaluation definitions for ACT15319

	Primary endpoint (RR) in patients with mCRPC	Primary endpoint (RR) in patients with mCRPC	Disease progression in patients with mCRPC
Assessment criteria	PSA	Radiographic objective response – soft tissue (bone lesions are not considered "non-measurable" lesions for RECIST; bone lesions will be assessed by bone scan only)	Radiographic objective response – bone scan
Timing of baseline assessment	Cycle 1 Day 1	Screening CT/MRI	Screening bone scan
Frequency of assessment	Once every 9 weeks	Once every 9 weeks	Once every 9 weeks
Response criteria	Decline ≥50%	RECIST 1.1	NA
Timing for confirmation of response	4 weeks	4 weeks	NA
Timing for confirmation of PD and stop treatment		4 weeks	6 weeks (2+2 rule)

Abbreviations: CT=computed tomography; mCRPC=metastatic, castration resistant prostate cancer; MRI=magnetic resonance imaging; NA=not applicable; PD=progressive disease; PSA=prostate-specific antigen; RECIST=Response Evaluation Criteria in Solid Tumors; RR=response rate.

Table 10 - Prostate Cancer Clinical Trials Working Group 3 criteria for progression at trial entry by disease manifestation

Variable	Progression criterion
Blood based	
PSA	Obtain sequence of rising values at a minimum of 1-week intervals.
	1.0 ng/mL is the minimal starting value if confirmed rise is only indication of progression unless pure small-cell carcinoma.
	Estimate pretherapy PSADT if at least 3 values available ≥4 weeks apart.
Imaging	
Nodes	Nodal progression sufficient for trial entry independent of PSA.
	Measurable lesions not required for entry.

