Bone Scan	At least 2 new lesions on first post-treatment scan, with at least 2 additional lesions on the next scan (2+2 rule).				
	If at least 2 additional new lesions are seen on the next (confirmatory) scan, the date of progression is the date of the first post-treatment scan, when the first 2 new lesions were documented.				
	For scans after the first post-treatment scan, at least 2 new lesions relative to the first post-treatment scan confirmed on a subsequent scan.				
	Date of progression is the date of the scan that first documents the second lesion.				
	Changes in intensity of uptake alone do not constitute either progression or regression.				
l	Report the proportion of patients who have not progressed at fixed time intervals (6 and 12 months).				

Abbreviations: CNS=central nervous system; mCRPC=metastatic, castration resistant prostate cancer; nmCRPC=nonmetastatic, castration resistant prostate cancer; PSA=prostate-specific antigen; RECIST=Response Evaluation Criteria in Solid Tumors.

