2.1.3.2 Secondary efficacy endpoint(s)

The secondary efficacy endpoints are:

- Tumor burden change: Tumor burden change is defined as the best percent-change from baseline in a sum of the diameters (longest for non-nodal lesion, short axis for nodal lesions) for all target lesions

Area under the curve (AUC) of percent-change from baseline in tumor burden is defined as the area under the percent-change from baseline versus time curve calculated using the trapezoidal method from the date of the first post-baseline assessment to the date of the last assessment

The time-adjusted AUC of percent-change from baseline in tumor burden is defined as AUC of percent-change from baseline in tumor burden divided by the duration of the assessment

- Duration of response: Duration of response is defined as the time from the date of first response (PR or CR in radiographic objective response, or PSA decline $\geq 50\%$ for patients with mCRPC) that is subsequently confirmed to the date of first disease progression or death, whichever occurs first. Disease progression includes radiographic disease progression or unequivocal clinical progression. The RECIST 1.1 criteria will be followed for assessment of radiographic disease progression in patients with NSCLC and the PCWG3 criteria will be followed in patients with mCRPC. For patients with mCRPC, radiographic progression includes progression by PCWG3 modified RECIST 1.1 for soft tissue and/or PCWG3 defined progression by bone scan. In the absence of disease progression or death before the analysis cut-off date or the date of initiation of a further anticancer treatment, the DOR will be censored at the date of the last valid response assessment not showing disease progression performed prior to initiation of a further anticancer treatment and the analysis cut-off date, whichever is earlier. DOR will not be calculated for patients who do not achieve a response

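### Protocol Section 12.3.2, read literally, and Table 9 apply 2+2 confirmation to all bone-scan-only progression, whereas Table 11 limits it to the first post-treatment scan

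*Protocol*

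**What the plan says.** Bone scans in mCRPC are repeated every 9 weeks from the end of Cycle 3, so most on-study scans come after the first post-treatment scan in any patient who stays on study. The protocol states how bone progression is confirmed in several places.

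- **Section 12.3.2, Disease assessment.** Progression based on bone scan only is confirmed by a repeat scan after 6 weeks using the 2+2 rule: "2 new lesions on first scan, with at least 2 additional lesions on the confirmatory scan; refer to Appendix A". The sentence also points to Section 6.7.1.
- **Appendix A, Table 9.** The row on confirming progression and stopping treatment gives, for bone scan, "6 weeks (2+2 rule", with no limit by scan.
- **Appendix A, Table 11.** The 2+2 rule is tied to the first post-treatment scan, and a second rule follows: "For scans after the first post-treatment scan, at least 2 new lesions relative to the first post-treatment scan confirmed on a subsequent scan".
- **Clinical Trial Summary, Duration of study period.** The 2+2 rule is glossed as "at least 2 new lesions on first post-treatment scan, with at least 2 additional lesions on the next scan". Later scans are not mentioned.
- **Section 6.7.1.** It gives the timing only ("or 6 weeks for bone progression in mCRPC in Appendix A") and no lesion count.

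Section 6.7.1 also says that patients with apparent progression on CT/MRI or "bone scan per PCWG3 criteria are allowed to continue until PD is confirmed providing" certain clinical conditions are met. Section 6.4 states: "The screening period for the cross-over part is 28 days from PD confirmation". For duration of response in mCRPC, SAP Section 2.1.3.2 counts "PCWG3 defined progression by bone scan" as radiographic progression.

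**The concern.** Section 12.3.2 is the visit-level instruction that sites use during treatment. Taken at its words, it demands at least two further lesions before any bone-scan-only progression counts as confirmed. Table 11 demands that only when the new lesions appear on the first post-treatment scan.

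The cross-references do not settle which rule governs. Section 6.7.1 has no lesion count and sends the reader to Appendix A. Appendix A holds both versions: Table 9 supports the broad reading and Table 11 the narrow one.

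Confirmed progression is a stopping criterion (Sections 6.7.1 and 11.1.1). Bone scan may be the main objective stopping signal for some patients, because measurable disease is not mandatory in mCRPC and PSA progression without radiographic progression does not stop treatment. Two sites with the same scans could reach different decisions on continuing study drug and on when the cross-over screening period begins.

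**Working it through.** The plan gives no figure to reproduce and no statistical formula applies. The check sets the two rules side by side on the same scan patterns.

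**Inputs.** Scheduled bone scans fall at weeks 9, 18 and 27 (every 63 ±7 days, Section 12.3.2). The first post-treatment scan is at week 9. The flowchart footnotes on bone scans (Sections 1.3 and 1.4) ask for the repeat scan at 6 weeks or more.

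| Pattern | Table 11 | Section 12.3.2, literal |
|---|---|---|
| At least 2 new lesions at week 9; at least 2 more on the repeat | Confirmed | Confirmed |
| 2 new lesions at week 9; fewer than 2 more on the repeat | Not confirmed | Not confirmed |
| 2 new lesions first seen at week 18 (relative to week 9); at least 2 more on the repeat | Confirmed | Confirmed |
| 2 new lesions first seen at week 18 (relative to week 9); same 2 persist, 0 or 1 more on the repeat | Confirmed | Not confirmed |

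The rules differ only in the last row: bone-scan-only progression that first appears after the first post-treatment scan, with 0 or 1 additional lesions at confirmation.

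**Length of any delay.** For the week-18 finding, the earliest repeat is week 18 + 6 = 24. Because the footnote sets a minimum and not a fixed interval, the scheduled week-27 scan can also serve, being 27 − 18 = 9 weeks later.

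- If week 27 is the confirmatory scan and shows at least 2 additional lesions, both rules confirm at week 27: 27 − 27 = 0 weeks of delay.
- If no further lesions ever appear, Table 11 confirms at the repeat scan and Section 12.3.2 never confirms bone progression.
- Between these ends, the delay depends on when further lesions appear and which scan the site accepts as confirmatory. The documents fix neither.

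**Endpoints.** Response in mCRPC is soft-tissue response or confirmed PSA decline, and Table 9 marks bone-scan response as not applicable. The primary response rate therefore does not use bone-scan confirmation. Protocol Section 9.6.2 and SAP Section 2.1.3.2 define bone progression by reference to PCWG3, whose criteria Table 11 sets out. PFS, radiographic PFS, duration of response and disease control at 6 months or longer would differ only if the analysis took progression status as recorded by sites under Section 12.3.2. The SAP Section 2.1.3.3 versions that require confirmed progression would then be the most exposed.

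**The case against.** The best defence is that Section 12.3.2 is incomplete and does not contradict Table 11. It invokes 2+2 as a named rule and points to Appendix A in the same parenthesis; the only full definition there is Table 11. Its 'first scan' can be read as shorthand for the first post-treatment scan, as the synopsis has it. Other operational text (the flowchart footnotes and Sections 12.4 and 12.5.1) asks only for a repeat scan and is compatible with Table 11.

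That reading is possible, but it does not dispose of the point. The instruction is triggered by bone-scan-only progression without limit by scan, and 'first scan' is paired with the confirmatory scan, so it naturally means the scan that raised the suspicion. Table 9 repeats the unqualified rule inside the appendix that is meant to resolve the matter. Even on the generous reading, Section 12.3.2 gives no rule for later scans and the same sentence has to be added.

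The defence does succeed in limiting the consequences. A reader might infer that sites must keep treating such a patient. The documents do not say so: Section 6.7.1 allows continuation under clinical-stability conditions, and Section 11.1.1 lets the investigator stop treatment at discretion. A reader might also work out a fixed delay in weeks or doses from the scan calendar. That is not supported either, because the repeat may be any scan at 6 weeks or more and the result depends on an unknown lesion pattern.

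**Conclusion.** The point holds as a minor inconsistency in a treatment-stopping rule. Section 12.3.2, read literally, and Table 9 apply 2+2 to all bone-scan-only progression; Table 11 does not. They give different answers for one type of patient: new bone lesions first seen after the first post-treatment scan that persist with 0 or 1 additional lesions.

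For that patient a site following Section 12.3.2 may continue study drug and, if Cohort A-2 opens, start cross-over screening later. The delay ranges from zero to bone progression never being confirmed. How often this would happen cannot be determined from the documents.

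It would be tempting to infer that the progression endpoints are biased. The documents do not establish that. Those endpoints refer to PCWG3 and nothing states that site-recorded status will replace it; they are also secondary or exploratory and descriptive. Nor is the synopsis wrong: it ties 2+2 to the correct scan and is only silent on later ones.

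The conclusion rests on reading Section 12.3.2 at its words and on Table 11 being the intended PCWG3 rule.

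**What to change.** In Section 12.3.2 and Table 9, limit 2+2 to new lesions on the first post-treatment scan and add the Table 11 rule for later scans, or replace both explanations with a citation of Table 11 alone. In the synopsis, add the later-scan rule and leave the rest. Optionally, have the SAP state that PCWG3 bone progression means both Table 11 rules with their dating.

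The cost is about one sentence in each place at the next amendment, with no extra scans. New-lesion counts per bone scan would need to be recorded if they are not already; the case report form is not among the documents, so this could not be checked.
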